## **10.2 – Procedures for recording, reporting and analyzing deviations from the Clinical Investigation Plan**

Protocol deviations shall be reported to the Sponsor regardless of whether medically justifiable or taken to protect the patient in an emergency.

Subject-specific deviations will be reported on the Labcorp Risk and Issues Management System (RIMS).

Non-subject specific deviations (e.g. unauthorized use of a study device by a physician who has not signed an investigator agreement, etc.) will also need to be reported to the Sponsor.

Investigators will also adhere to procedures for reporting study deviations to their Ethics Committee or IRB in accordance with their specific reporting policies and procedures.

For reporting purposes, the Sponsor classifies study deviations as important or non-important. Important deviations are defined as changes in the conduct of the trial from that specified in the protocol that compromise the subject's rights, safety, or well-being, or the completeness, accuracy, reliability or scientific integrity of the study data. The following deviations are considered to be important:

1. Enrollment of a patient without written consent
2. Failure to report SAEs
3. Crossovers between the groups
4. Use of other energy than RF for ablation (cryo/chemical)
5. Ablation other than antral PVI in the Anatomical arm for index procedures (e.g. lines other than ICT, EGM ablation, PV encirclement other than antral),
6. Ablation other than PVI ± lines (as defined in 5.3.7 – Redo procedure) in the Anatomical arm for redo procedures,
7. Failure to terminate AF with incomplete mapping in the Tailored group (mono atrial mapping, too short mapping < 20 minutes),
8. Failure to terminate AF with incomplete ablation in the Tailored group, leaving dispersion areas not ablated, without valid justification (for safety reasons at operator's discretion),
9. Failure to terminate AF without a mandatory second mapping/ablation cycle in the Tailored group,

Deviations not classified as important will be considered non-important. Protocol deviations will be classified by the Steering Committee in a blinded fashion. Patients presenting with at least one important deviation will be excluded from the Per-Protocol (PP) analysis.

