#### AF induction

If the patient does not present in spontaneous sustained AF at the beginning of the procedure, sustained AF must be induced by atrial burst pacing, either with or without the additional infusion/injection of isoproterenol (20 microg/min) ± adenosine (according to site practice).

In the Tailored group, should AF not be inducible or be inducible and non-sustained, the patient will undergo conventional AF ablation per physician discretion. This patient/case will not be considered in the per-protocol analysis.

 <small>ARTIFICIAL INTELLIGENCE SERVING HEART DISEASE</small>	CLIPL-01-002-E	CONFIDENTIAL
	CLINICAL INVESTIGATION PLAN	F 09 XX 01 Rev.A

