### Ablation procedure in the Tailored group

In the Tailored group, the procedure endpoint is sinus rhythm conversion by ablation at dispersion regions mapped during AF and potential subsequent AT(s).

Once mapping is complete:

- 1) The operator starts by ablating all dispersion areas. Tailored-PV-encircling along dispersion regions is recommended during dispersion areas ablation (cf. Figure 2). Ablation should always be done in a manner to either cover the dispersed electrograms or encircle a large area of dispersed electrograms (cf. Figures 3 and 4)
- 2) The operator then completes the isolation of the 4 PVs
- 3) The electrical connection of the 4 PVs is checked at the end of the procedure according to each site routine practice. Additional perivenous ablation can be performed to electrically disconnect the connected PV(s).

 Tailored-PVI or Tailored-PV-encircling corresponds to PVI or PV-encircling along dispersion areas around the PVs in order to optimize the flow of the procedure.

[figure not shown]

Figure 2: Tailored-PVI after Tailored-PV-encircling

In case of failure to terminate AF after ablation of all dispersion areas, at least one re-mapping/re-ablation is mandated, and two complete re-mappings are recommended. If the patient did not convert to sinus rhythm with ablation, a DC electrical cardioversion is performed.

If sinus rhythm is restored before ablation at all dispersion areas, the completion of the ablation set is mandatory, except in the atrial regions positioned close to the esophagus, phrenic nerve, AV node and/or sinus node. This list is not exhaustive, the operator can identify and document any other potentially hazardous areas for ablation.

When a sustained AT results from the ablation of all dispersion areas, mapping and ablation of AT must be performed with the use of activation maps  $\pm$  VX1  $\pm$  pacing maneuvers.

In case of linear ablation performed for macro-reentry (roof, perimital, cavo-tricuspid isthmus (CTI) flutter), lines should be validated by establishing a post-ablation bidirectional block. The impossibility of performing the line validation must be documented. No line validation is required without documented macro-reentry.

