## 6.2 – Sample size

The primary endpoint is freedom from AF, 12 months after a single ablation procedure. As observed from previously published studies in patients receiving PVI alone for persistent AF, it could be assumed that at most 62% of the patients in the anatomical group will be free from AF at the end of follow-up. A previous study conducted on VX1 suggested that at least 77% of the patients of the tailored group may be free from AF at the end of follow-up (i.e. Hazard Ratio (HR) 0.547). In order to confirm these results prospectively in this study, 292 patients (146 in each group) are required to show that time to AF is significantly different between groups (Log-Rank test for a one-sided superiority trial, significance level  $\alpha=0.025$ , statistical power of 80%, under the assumption that the hazard rates are proportional).

Assuming a drop-out rate of 22% (no ablation performed or loss to follow up), **374 patients are required overall** (187 in each group).

Sample size calculations performed using SAS Proc Power TwoSampleSurvival (SAS Institute Inc., Cary, NC)

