## 6.3 – Degree of significance and power of the clinical investigation

Assumptions for the superiority endpoint include a one-sided 0.025 alpha level and 80% power.

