4.1.3 The Per-Protocol Population (PP)

The Per-Protocol (PP) analysis set will include only those subjects of either given treatment arm defined as the treatment actually received at the start of the study, and will consist of subjects who met all the inclusion criteria, none of the exclusion criteria, were successfully treated with an index procedure, had no important protocol deviations, and attended the scheduled follow-up visits (did not miss more than one mandatory Holter recording, and TTM compliance >50%).

The PP analysis set will also be used to evaluate endpoints already evaluated using the mITT as the primary analysis set, thus serving as supportive analyses to that of the mITT efficacy analysis.

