4.2.4 Sensitivity Analyses of Primary Endpoint

The Primary Endpoint Analysis will additionally be conducted in the PP population.

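### Two Tailored-arm exclusions from the per-protocol set apply only when AF fails to terminate, so the supportive analysis of the primary endpoint selects on acute outcome in one arm

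*Protocol*

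**What the plan says.** **Deviation list.** Protocol 10.2 numbers nine important deviations. Item 7 is "Failure to terminate AF with incomplete mapping in the Tailored group", meaning one atrium only or under 20 minutes. Item 8 is failed termination with dispersion areas left unablated without a valid safety reason. Item 9 is failed termination without the mandatory second mapping and ablation cycle. All three apply to the Tailored group only. One important deviation removes the patient from PP, and anything not classified as important is non-important. The Anatomical items (5 and 6) concern which lesions were delivered. On procedure, 10.2 adds: "Protocol deviations will be classified by the Steering Committee in a blinded fashion".

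**Index procedure.** Protocol 5.3.4 attaches the same termination condition to incomplete mapping. For ablation, however, it makes completing the set mandatory even if sinus rhythm returns early, apart from hazardous regions. A second cycle is required only when AF has not terminated after all dispersion areas are ablated. On acute success: "In the Tailored group, the procedure endpoint is sinus rhythm conversion by ablation at dispersion regions". In the Anatomical group the procedure endpoint is isolation of all four veins. Any patient not in sustained AF must be induced, but for Tailored patients whose AF is non-inducible or non-sustained: "This patient/case will not be considered in the per-protocol analysis". No such sentence exists for Anatomical patients.

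**SAP.** Section 4.1.3 admits patients who "were successfully treated with an index procedure, had no important protocol deviations", and redefines neither term. Section 4.2.4 reads in full: "The Primary Endpoint Analysis will additionally be conducted in the PP population".

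**The concern.** Take two Tailored patients, each mapped for 15 minutes. One terminates and stays in PP; the other does not terminate and leaves. They received the same incomplete work, and only a post-randomisation result separates them. The same holds for dispersion areas left without justification. If patients whose AF does not terminate recur more often, the rule removes poor-prognosis patients from the Tailored arm and leaves the Anatomical arm as it is.

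The PP analysis is meant to show that the mITT result is robust. A check that can lean towards the experimental arm by construction gives weaker reassurance than it appears to. The same set supports the two secondary efficacy endpoints (SAP 4.3.2) and is one of the safety analysis sets (SAP 4.5).

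**Working it through.** **1. The plan's own figure.** Inputs from Protocol 6.2 and 6.3: "at most 62% of the patients in the anatomical group will be free from AF"; 77% in the Tailored group; "Assumptions for the superiority endpoint include a one-sided 0.025 alpha level and 80% power".
- HR = ln(0.77)/ln(0.62) = 0.547, as stated.
- A log-rank calculation by the Lakatos method (exponential survival, fixed follow-up) gives N = 291.8, so 292, with about 89 events.
- 292/0.78 = 374.4, against the stated 374.

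The planning figures reproduce, so 62% and 146 per arm are used below.

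**2. Who leaves PP, by work done and acute result (Tailored arm)**

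| Work done | AF terminated | AF not terminated |
|---|---|---|
| Mapping incomplete | stays | leaves (item 7) |
| Areas left, no justification | stays | leaves (item 8) |
| No second cycle | stays; none was required | leaves (item 9) |

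In rows 1 and 2 the same shortfall is treated differently according to outcome. Row 3 is different, because a terminator owes no second cycle.

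**3. Size with no true effect.** The documents give no rate of incomplete work, no termination rate and no outcome gap by termination. All three are assumptions:
- t = share of Tailored patients whose AF terminates
- q = share with a shortfall under items 7 to 9 taken together, unrelated to prognosis
- g = AF-free rate in terminators minus that in non-terminators

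With S = 0.62 in both arms:
- share removed: x = q(1 − t)
- rate in those removed: S − t·g
- Tailored PP rate: [S − x(S − t·g)]/(1 − x), so the shift is x·t·g/(1 − x)

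| t | g | q | x | Shift (points) |
|---|---|---|---|---|
| 0.9 | 0.10 | 0.05 | 0.005 | +0.05 |
| 0.9 | 0.10 | 0.10 | 0.010 | +0.1 |
| 0.7 | 0.20 | 0.20 | 0.060 | +0.9 |
| 0.5 | 0.30 | 0.30 | 0.150 | +2.65 |
| 0.6 | 0.30 | 0.40 | 0.160 | +3.4 |

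Two sets of ranges were tried. With t 0.5–0.9, g 0.1–0.3 and q 0.05–0.3, the shift is +0.05 to +2.65. With t 0.6–0.9, the same g and q 0.1–0.4, it is +0.1 to +3.4.

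**4. Effect on the PP test, middle case.**
- Tailored PP rate = (0.62 − 0.06 × 0.48)/0.94 = 0.629.
- HR = ln(0.629)/ln(0.62) = 0.970.
- Tailored n = 146 × 0.94 = 137.2. Events = 137.2 × 0.371 + 146 × 0.38 = 106.4. Tailored share of patients = 0.485.
- Mean of the test statistic = −ln(0.970) × √(106.4 × 0.485 × 0.515) = 0.157.
- One-sided error = Φ(0.157 − 1.960) = 3.6%, against 2.5%.

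The same steps give 2.6% at the +0.05 end, 6.6% at +2.65 and 8.5% at +3.4.

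**5. Check on the cause.** If completeness counted whatever the acute result, and were unrelated to prognosis, the Tailored PP rate would stay at 62% and the error at 2.5%. If g = 0 the rule causes no shift. If g were negative it would work against Tailored.

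**The case against.** **What stands.** PP is only supportive. The conclusion rests on mITT, which keeps these patients. SAP 4.2.5 also varies the AF-duration covariate, and SAP 6.3 promises missing-data analyses, though without a method. The upper end of the range needs 16% of the Tailored arm (0.16 × 146, about 23 patients) to have an important deviation, whereas Protocol 10.3 prompts an assessment after two at one site. Every gap tried was positive, while Protocol 4.3 treats the relation between acute and long-term success as something to assess. The Anatomical rate was held at 62%, although items 5 and 6 also remove Anatomical patients.

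**Stronger readings that a reader might infer, and why they fail**
- *Every Tailored non-terminator leaves PP as not successfully treated.* The shift would then be (1 − t)·g: 1 to 12 points for t from 0.6 to 0.9, and 15 at t = 0.5. But items 7 to 9 would then be redundant as PP exclusions, and the SAP's mention of an index procedure reads more naturally as having received it. The arithmetic also uses AF termination, whereas the Tailored procedure endpoint is sinus rhythm conversion, a separate outcome in Protocol 4.3. The fair request is a definition.
- *Item 9 has the same fault as items 7 and 8.* It repeats a requirement that exists only after failed termination. Applying it to everyone would remove compliant terminators and create a new selection.
- *Blinded classification is impossible.* The items name the arm, so blinding to arm is hard to achieve. The protocol does not say what the committee is blind to, and blinding to follow-up outcome is feasible.
- *The non-inducible exclusion also removes poor responders.* These patients receive conventional ablation, so leaving PP is ordinary logic. The problem is only that one arm is affected, and the direction of any bias is unknown.
- *A favourable PP result could come from selection alone.* Shifts of this size against a planned 15 points do not show that.

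**Conclusion.** The point holds for items 7 and 8. The PP set conditions on acute AF termination in the Tailored arm, and no Anatomical rule does so. With items 7 to 9 taken together and no true effect, the shift is about 0.05 to 3.4 points, with a middle case of +0.9 points and one-sided error near 3.6%. Items 7 and 8 alone account for no more than that under these assumptions. Every input beyond 62% and 146 per arm is assumed, and the direction depends on non-terminators recurring more often. The bias is small to moderate and confined to supportive analyses. It is still worth removing, because PP is the only entry under SAP 4.2.4 and the correction is cheap.

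**What to change.** Amend the PP definition in SAP 4.1.3, which prevails over the protocol (SAP section 3):

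- **(a) Items 7 and 8.** For PP membership, define incomplete mapping and unjustified incomplete ablation by the work done, whether or not AF terminated, and keep the safety justification. Derive them from the procedure data in Protocol Table 7 (mapping times, mapping picture, justification for untreated regions). The deviation log may omit shortfalls in patients who terminated.
- **(b) Item 9.** Leave it as written, and report PP with and without that exclusion.
- **(c) Successful treatment.** State that it means the assigned index ablation was delivered, in both arms.
- **(d) Non-inducible or non-sustained AF.** Induction is required of all patients not in sustained AF and precedes ablation, so apply this PP exclusion to both arms, or report PP both ways. This needs the induction result to be recorded in both arms.
- **(e) Classification.** State that deviations are classified before outcome data are seen.

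The cost is SAP wording and one or two extra PP runs. For (a), Table 7 already collects the data. PP membership changes slightly. PP may still be biased if completeness is itself prognostic, so it should stay supportive. None of this changes how patients are treated.

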#### Re-ablation procedure in Anatomical group

During a repeat ablation in the Anatomical group, PV reconnections will be checked, and potentially reconnected PV will be re-isolated.

A maximum of two additional anatomical lines are allowed (0, 1 or 2 lines): roof and/or mitral isthmus and/or CTI lines or posterior box isolation (no other lines are allowed).

The redo procedure endpoint is *isolation of all four PVs and lines validation*.

In case of regularization into AT during anatomical re-ablation, mapping (without VX1) and ablation of the AT is allowed. If the repeat procedure is performed for an AT, it can be mapped (without VX1) and ablated.

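### For the single-procedure endpoints, membership of the per-protocol set depends on redo conduct and monitoring after the first AF event, when the patient's outcome is already fixed

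*Protocol*

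**What the plan says.** Protocol 10.2 gives the exclusion rule: "Patients presenting with at least one important deviation will be excluded from the Per-Protocol (PP) analysis". The rule has no time limit. Item 6 of its list of important deviations reads "Ablation other than PVI ± lines (as defined in 5.3.7 – Redo procedure) in the Anatomical arm for redo procedures". Items 7 to 9 concern failure to terminate AF in the Tailored group after incomplete mapping, incomplete ablation or no second cycle. They do not say whether they cover the index procedure only, and Protocol 5.3.7 has the Tailored redo follow the index approach.

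SAP 4.1.3 also requires that the patient "did not miss more than one mandatory Holter recording, and TTM compliance >50" percent. It gives no denominator and no stop at the first event. Protocol 6.1 asks for attendance at all visits; SAP section 3 says that the SAP prevails.

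SAP 4.2.4 then states: "The Primary Endpoint Analysis will additionally be conducted in the PP population". Nothing else is listed there. SAP 4.3.2 does the same for the two secondary efficacy endpoints. The primary analysis is in the mITT set.

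For Anatomical redos, Protocol 5.3.7 states: "In case of regularization into AT during anatomical re-ablation, mapping (without VX1) and ablation of the AT is allowed".

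**The concern.** The primary outcome is settled at the first confirmed AF recurrence between months 3 and 12. What happens afterwards cannot change the patient's status or event time. A set that selects on later conduct can remove patients who are known to have failed.

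Item 6 can be met only by a patient who has had a redo. Redos follow AF or AT recurrence (Protocol 5.3.6), and a redo with the patient in spontaneous AF is itself a primary failure (SAP section 5). The monitoring rules act in a similar way: a patient with confirmed AF at month 4 may stop weekly recordings or skip later Holters, and is then excluded although nothing about the primary outcome is missing.

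At stake is the reading of the supportive analysis. If PP and mITT disagree, the difference may reflect adherence to the procedure or selection after the outcome, and the plan offers no way to tell these apart.

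**Working it through.** **Plan figures first.** Protocol 6.2 assumes that "at most 62% of the patients in the anatomical group will be free from AF at the end of follow-up" and that "at least 77% of the patients of the tailored group may be free from AF at the end of follow-up". Protocol 6.3 adds: "Assumptions for the superiority endpoint include a one-sided 0.025 alpha level and 80% power".
- HR = ln(0.77)/ln(0.62) = 0.547, as stated.
- A log-rank power calculation with exponential survival and fixed follow-up gives 79.75% at N = 290 and 80.02% at N = 292, so 292 (146 per arm) is reproduced.
- 292/0.78 = 374.4, against the stated 374.
- Planned failures: 146 × 0.38 = 55.5 Anatomical and 146 × 0.23 = 33.6 Tailored.

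**Redo item (item 6).** SAP 6.9 expects 22% to 33% of patients to have a second procedure, not split by arm or rhythm. Applied to 146, this is 32 to 48 Anatomical patients. Assume that 10% to 20% of these redos meet item 6 and that all were for AF. Then 3 to 10 failures leave (0.10 × 32 = 3.2; 0.20 × 48 = 9.6).
- Remove 3: AF-free = 0.62 × 146/143 = 63.3%; HR = ln(0.77)/ln(0.633) = 0.57.
- Remove 10: AF-free = 0.62 × 146/136 = 66.6%; HR = ln(0.77)/ln(0.666) = 0.64.

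**Opposite pull (items 7 to 9).** Take no true effect, 62% in both arms. Removing an assumed 2, 5 or 8 Tailored patients who later fail gives HR 0.97, 0.93 or 0.88. On the same footing, removing 3.2 to 9.6 Anatomical failures through item 6 gives HR 1.05 to 1.17.

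**Monitoring rule, one patient.** Assume that TTM compliance is counted over about 52 weekly transmissions (SAP section 1). Perfect transmission to an event at week 14, then stopping, gives 14/52 = 27%, so the patient is dropped. Stopping before week 26 gives less than 26/52 = 50%. Missing both the 6- and 12-month Holters also excludes.

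**Monitoring rule, by arm.** Take a constant hazard from day 98 (end of blanking, SAP 6.2) to day 365, h = −ln(S)/267. Week 26 is day 182, which is 84 days later.
- Anatomical: 1 − exp(−84h) = 0.140, or 0.140/0.38 = 37% of events.
- Tailored: 1 − exp(−84h) = 0.079, or 0.079/0.23 = 34% of events.

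If a share q of these early-event patients stops, AF-free becomes S/(1 − q × early-event proportion):

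| q Anatomical | q Tailored | Anatomical AF-free | Tailored AF-free | HR |
|---|---|---|---|---|
| 10% | 10% | 62.9% | 77.6% | 0.546 |
| 30% | 30% | 64.7% | 78.9% | 0.545 |
| 30% | 10% | 64.7% | 77.6% | 0.582 |
| 10% | 30% | 62.9% | 78.9% | 0.512 |

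**The case against.** PP is declared supportive and mITT carries the primary test, so no error rate, sample size or claim of superiority rests on PP. SAP 4.2.5 lists further analyses of the primary endpoint, and SAP 6.3 promises missing-data analyses. This limits the consequence. But the 4.2.5 analyses only change how AF duration enters the model, and those in 6.3 are not specified. PP remains the only named sensitivity analysis.

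Three stronger readings are tempting, and the documents do not support them.

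A reader might infer that PP drops patients because they failed. No rule does that. A further deviation or missed monitoring is always needed, the monitoring rule also applies to event-free patients, and SAP 4.2 treats a redo for a non-AF indication as compatible with primary success. Excluding such a patient would remove an AF-free Anatomical patient.

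A reader might infer that the redo rule acts on one arm only and so biases PP against the Tailored arm. That is right for item 6 alone when the redo was for AF. Items 7 to 9 name only the Tailored arm and may reach Tailored redos, while crossovers and non-RF energy (items 3 and 4) apply to both arms at any time.

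A reader might count every recurrent patient who stops monitoring as excluded. With 20% stopping, that would give 0.62/(0.62 + 0.38 × 0.8) = 67.1% against 0.77/(0.77 + 0.23 × 0.8) = 80.7%. This is too high. One missed Holter is tolerated, and a patient with good TTM who stops after about week 26 still passes.

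On item 6 and AT ablation, one can argue that the reference to 5.3.7 brings in everything that section permits. That is plausible, but the item names only PVI and lines, so the two texts still need to be reconciled.

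**Conclusion.** The point holds as a defect in a supportive analysis. For the single-procedure endpoints, neither Protocol 10.2 nor SAP 4.1.3 stops at the first event, so patients with a known outcome can be removed for what they or their operators do later.

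The net direction is unknown. Item 6 alone moves the HR from 0.547 to between 0.57 and 0.64, if 3 to 10 Anatomical AF failures are removed. The Tailored-only items may offset or exceed this. The monitoring rule lifts AF-free rates to about 63-65% and 78-79%, and leaves the HR near 0.546 if stopping is equal by arm. It matters to the contrast only if stopping differs: 30% against 10% gives 0.58 or 0.51.

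All deviation and stopping rates are assumptions, and so is the 52-week TTM denominator. The change is worth making because the rule is explicit and correcting it is cheap.

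**What to change.** In SAP 4.1.3:
- **Single-procedure endpoints, deviations.** Exclude only for eligibility failures and important deviations at or before the index procedure.
- **TTM compliance.** Count it from the index procedure to the first endpoint event or censoring, with only the weeks up to then in the denominator.
- **Holters.** Count as missed only those whose window closed before that date. Keep the 3-month Holter: its window closes at 3 months (Protocol Table 8), before day 98, so a count starting at day 98 would lose it.
- **One-or-two-procedure endpoints.** Apply redo deviations here only, up to that endpoint's own event, with parallel rules in both arms.
- **Clarify.** State whether items 7 to 9 reach Tailored redos, and reconcile item 6 with what Protocol 5.3.7 allows for AT at an Anatomical redo.

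The cost is SAP wording and some programming, since PP membership becomes endpoint-specific. No new data are needed. The PP set becomes slightly larger and will include some patients censored early. Because the SAP prevails over the protocol, a change there is enough for the analysis.
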